To identify telerehabilitation as a strategy for optimizing care and access to public rehabilitation services.

METHODS

In order to answer the research objectives, a randomized controlled trial study was chosen. This is a pilot study that will be developed through the proposal of telerehabilitation sessions for patients on a waiting list, with a medical prescription, for Occupational Therapy care at the IMREA FMUSP, linked to the Lucy Montoro Rehabilitation Network.

A convenience sample will be used (20 users, divided equally into two groups), considering that patients awaiting care will be subject to the research eligibility criteria and will be selected in descending order (selected in reverse chronological order from the waiting list) to allow sufficient time for the intervention. If a study participant, regardless of the group to which they belong, is called to begin in-person Occupational Therapy care, a final assessment will be applied, concluding the follow-up.

Data collection for initial and final assessments will be conducted by an independent researcher, not involved in the study, allowing for a single-blind study. Participants will be divided into two groups using randomization: intervention and control. The first group (intervention) will participate in one 45-minute session per week for eight weeks. During this

RESEARCH PLAN

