time, participants will receive guidance and perform therapeutic activities to improve occupational performance. The second group (control) will remain on the waiting list, without a specific intervention, as they were already waiting for care. Both groups will undergo initial assessments in the first session and final assessments in the last session. Jerry Dallal's randomization tool (Dallal, 2020) will be used to classify participants into the first and second groups. Allocation, at a 1:1 ratio, will be conducted by an independent researcher who will not participate in data collection or statistical analysis. The concealed allocation will be implemented using sequentially numbered, opaque, and sealed envelopes. A blind evaluator will open the sealed envelopes after the Informed Consent Form (ICF) has been signed and will conduct the evaluation of the participant in person. Those participants selected by lottery, belonging to the intervention group, will be given a schedule with the dates and topics that will be addressed in each session. Participants in the control group will sign the ICF and complete the structured questionnaire and rating scales.

The following research protocols will be used as data collection instruments: Katz Scale (Lino et al., 2008) for assessing ADLs; Scale of Instrumental Activities of Daily Living (Dos Santos; Júnior, 2008) for measuring performance in IADLs; and Motor Activity Log (MAL) for assessing hand motor function (Saliba et al., 2011). The study will be conducted according to the Consolidated Standards of Reporting Trials (CONSORT) and the Standard Protocol Items: Recommendations for Interventional Trials (SPIRIT).

Participants will also be given a structured sociodemographic questionnaire, developed by the researcher, to collect demographic data, including age, sex, educational level, and other data. Similarly, clinical data will be collected, such as the duration of hemiplegia, laterality of the affected body, etiology, hand preference, risk factors, and motor stages according to the Brunnstrom model (Naghdi, 2010). The questionnaire will be administered by the independent researcher at the time of randomization.

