Thus, based on the research instruments presented, the research will be structured in five stages: i) recruitment of eligible patients; ii) randomization; iii) application of scales and structured questionnaire (intervention and control groups); iv) occupational therapy intervention via telerehabilitation (intervention group); v) final evaluation (intervention and control groups); vi) data processing and analysis.

Inclusion criteria

Adult patients, clinically stable, regardless of sex, race/color, aged 18 years or older, who present with sequelae of stroke, regardless of the Rankin scale score (Rankin, 1957), on a waiting list and according to medical indication for Occupational Therapy care at IMREA HCFMUSP. Individuals must also have access to a computer, tablet, and smartphone with an internet connection that allows for video calls, understand the Portuguese language, and have the assistance of a caregiver during therapy sessions, if necessary.

Exclusion criteria

RESEARCH PLAN

Clinically unstable patients, such as frail elderly individuals with decompensated chronic diseases and high-risk pregnant women **and individuals** under 18 years of age who are not on a waiting list for Occupational Therapy at IMREA HCFMUSP, in accordance with medical indication. Individuals who do not have access to a computer, tablet, or smartphone with an internet connection, and who do not have a caregiver when needed during therapy sessions, will also be excluded.

RISK ANALYSIS

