The research presents a low risk of harm to participants, as it involves remote guidance, not exposing the user to any type of invasive procedure or risk associated with travel for appointments. However, the nature of stroke can result in significant variations in the cognitive and physical abilities of patients, which may interfere with adherence to and development of therapeutic interventions through telerehabilitation. Regarding the proposal to conduct remote appointments via video call platforms, there is a risk that sessions may be compromised due to technical and connection problems at the time of the sessions, potentially leading to difficulties in understanding and hindering the visualization and interpretation of instructions, inhibiting or hindering participation. Interruption of remote appointments will occur due to health problems and personal issues of the patient that prevent their participation; recurring technical issues that prevent the patient from accessing sessions; lack of interest from the research participant in continuing treatment; as well as the start of in-person Occupational Therapy appointments. To minimize such risks, a set of measures and/or procedures will be taken to ensure the privacy, confidentiality, and security of participants and their information. These are: i) data collection through scales and the structured questionnaire will be carried out manually, and only the researchers involved in the research will have access; ii) data collected manually will be digitized and stored on institutional servers; iii) personal information of participants related to the information provided will not be part of the research records, including any information that could be used to establish, identify, or reveal the participant's identity, or any other data that may be requested by the participant will be discarded from the research records; iv) depending on the degree of difficulty the patient has in performing the activities through telerehabilitation, it will be necessary for them to have a family member or caregiver present during the session; v) the participant will have complete freedom not to participate or to withdraw their consent at any time, even after the conclusion of the research, without any penalty, and will have confidentiality and privacy. vi) Nevertheless, in the event of harm or distress, the researcher is committed to providing support and referring participants to the physician responsible for the patient, without any expenses for the participants.

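### The plan does not say whether or when participants whose remote sessions stop early have the final assessment, so outcomes may be lost or taken off schedule unequally between the arms

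*Combined protocol and SAP*

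**What the plan says.** RISK ANALYSIS lists four kinds of reason for interrupting the remote sessions. It begins "Interruption of remote appointments will occur due to health problems and personal issues of the patient that prevent their participation", continues with "recurring technical issues that prevent the patient from accessing sessions", and ends with "lack of interest from the research participant in continuing treatment; as well as the start of in-person Occupational Therapy appointments".

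METHODS has an early-assessment rule for one of these only, and it covers both arms. It applies when someone "is called to begin in-person Occupational Therapy care, a final assessment will be applied, concluding the follow-up". For everyone else the rule is: "Both groups will undergo initial assessments in the first session and final assessments in the last session". The list of study stages in METHODS and the TIMELINE table both include a final evaluation for the intervention and control groups.

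Appendix 5 sets out the full course in the intervention group: service 1 is the in-person baseline assessment, services 2 to 9 are the eight remote sessions, and service 10 is the in-person final assessment. Controls stay on the waiting list and have no sessions.

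DATA ANALYSIS compares group means as observed at the assessments, by t-test or Wilcoxon test. It defines no analysis population and no handling of missing outcomes. RISK ANALYSIS also lets any participant withdraw consent at any time.

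**The concern.** The authors saw that one kind of early exit needed a rule for the outcome and wrote one. The other three kinds have none. For these participants the final assessment is tied to an event, the last session or service 10, that has no defined date once sessions have stopped.

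Three features make this more than a drafting gap. Session-related stopping can occur only in the intervention arm. Its reasons (ill health, failed connections, loss of interest) may relate to how well the person is doing. RISK ANALYSIS itself expects differences in cognitive and physical ability to interfere with adherence, and entry is open at any Rankin score. Finally, the analysis uses whatever was observed, so nothing later in the plan would repair an outcome that was lost or taken at a different time.

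What is at stake is a comparison between those who got through the remote course and nearly all controls. The participants for whom telerehabilitation did not work are also central to the specific objective on challenges and limitations, and they are the ones most likely to go unmeasured.

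**Working it through.** **1. Reasons set against rules**

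| Reason for interruption (RISK ANALYSIS) | Can it interrupt anything in a control? | Early final assessment ordered (METHODS)? |
|---|---|---|
| Health or personal problems | No, there are no sessions | No |
| Recurring technical problems | No | No |
| Loss of interest in continuing | No | No |
| Start of in-person therapy | Controls can be called too | Yes, in either arm |

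Of the four kinds, one has a rule and three do not.

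**2. What the default rule gives an early stopper**

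Take a participant whose sessions stop after service 4 in Appendix 5, that is, after three of the eight remote sessions. The text allows three readings: assess at that point, after about three weekly sessions rather than eight; assess when service 10 would have fallen due; or do not assess. The first gives an off-schedule outcome, the second an on-schedule one, the third a missing one. Nothing in the plan chooses between them.

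**3. Size of the bias if outcomes are lost**

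The plan gives no dropout rate, SD or effect size, so it has no figure to reproduce. From METHODS: 20 participants, 10 per arm. Assumed: m intervention participants are missing, no control is missing, and those missing are worse than completers by D SD.

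If completers average C, the full-arm mean is [(10 − m)C + m(C − D)]/10 = C − mD/10. The observed mean is therefore too favourable by (m/10) × D.

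| m | D = 0.5 | D = 1.0 |
|---|---|---|
| 1 | 0.05 SD | 0.10 SD |
| 2 | 0.10 SD | 0.20 SD |
| 3 | 0.15 SD | 0.30 SD |

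**4. Worst case**

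Suppose exactly the lowest scorers are lost and scores are normal. The expected values of the three lowest of 10 standard normals are about −1.539, −1.001 and −0.656. The remaining mean rises by:

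- one lost: 1.539/9 = 0.17 SD
- two lost: (1.539 + 1.001)/8 = 2.540/8 = 0.32 SD
- three lost: (2.540 + 0.656)/7 = 3.196/7 = 0.46 SD

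A simulation of 2,000,000 samples of 10 gives 0.171, 0.318 and 0.457.

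These shifts are in the favourable direction. On IADL and the Motor Activity Log that means a higher mean. On Katz, where 0 is independent and 6 is dependent in all functions, it means a lower one.

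**5. How likely, and how large beside the noise**

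With an assumed stopping probability p per intervention participant, the chance that at least one of 10 stops is 1 − (1 − p)^10: 40%, 65%, 89% and 97% for p = 5%, 10%, 20% and 30%. This is the chance of stopping sessions, not of losing the outcome.

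With 8 against 10, the standard error of the difference is √(1/8 + 1/10) = 0.47 SD. The 0.10–0.20 SD bias for two losses is therefore about 0.2 to 0.4 of a standard error. Precision is little affected: at an assumed two-sided 5% level and 80% power, the detectable difference goes from 1.33 SD with 10 per arm to 1.37, 1.42 and 1.48 SD with 1, 2 and 3 losses.

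**The case against.** The strongest reply is that the plan never says these participants leave the study. RISK ANALYSIS speaks of interrupting remote appointments, not of ending follow-up. METHODS and TIMELINE plan a final evaluation for both groups and exempt nobody. The rule for in-person care can be read as bringing the assessment forward in one situation, not as the only way an early stopper is ever assessed. Appendix 5 describes a full course and is silent on shortened ones. All of this stands. A reader might infer that participants stopped for health, technical or motivational reasons are sent away without an outcome, but the documents leave the matter open. They do not prescribe the loss.

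A reader might also infer that missing outcomes can arise only in the intervention arm. That is true of interrupted sessions but not of outcomes. Any participant may withdraw consent, and a control may miss the in-person final visit through illness or lack of interest, with no rule for that case either. Losses among controls could offset or even reverse the bias, so its direction is probable and not certain.

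The figures are open to challenge too. Technical and personal reasons need not track function, and a normal model fits poorly for a 0 to 6 count or for seven items scored 1 to 3. The worst-case row is a ceiling and should not be read as an expectation.

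What survives is narrower: assessment has no defined time after session-related stopping, that kind of stopping belongs to one arm, and the analysis has no rule for what is missing.

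**Conclusion.** The gap is real. Three of the four kinds of interruption have no stated assessment time, and the default timing does not resolve it. Outcomes may be lost or taken off schedule, unequally between the arms and in relation to prognosis. With observed means compared, the likely direction of any bias is in favour of the intervention.

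On the assumed gap of 0.5 to 1.0 SD the bias runs from 0.05 to 0.30 SD for one to three losses, with a ceiling of 0.17 to 0.46 SD. Both ranges rest on assumed inputs and on no loss among controls. Random error remains larger than this bias in a pilot of 20, but the bias can be reduced at the design stage, whereas an outcome not collected cannot be recovered in the analysis. The documents do not support saying that the randomisation is undone or that the result must favour the intervention.

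**What to change.** State in METHODS and RISK ANALYSIS that interruption of remote appointments is not withdrawal from the study. Then add:

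- Every randomised participant in either arm who has not withdrawn consent to follow-up has the final Katz, IADL and Motor Activity Log assessment at the planned calendar time after baseline, and that time is written down. This also gives controls a date, since they have no last session.
- The one exception is the call to in-person Occupational Therapy, where the existing early-assessment rule stays unchanged.
- If a participant cannot attend, the same independent evaluator applies the scales by video or telephone, under the same rule in both arms, and the mode is recorded.
- In DATA ANALYSIS: participants are analysed in the group to which they were randomised, and the number of missing outcomes and the reasons for them are reported by arm.

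The listed reasons for interruption stay as they are.

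The cost is a few sentences and a few extra assessments of 60 minutes each. The downside is that some final scores would be taken remotely rather than in person, which is why the mode should be recorded.

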
BENEFITS

The benefit of this research to individuals diagnosed with stroke and to occupational therapists working in the rehabilitation field within the Brazilian Unified Health System (SUS) is direct. For patients, it represents a possible structuring of another healthcare pathway in the

RESEARCH PLAN

rehabilitation process. For professionals, the research is linked to expanding knowledge about the use of telehealth for rehabilitation interventions within the SUS. The benefits for other professional categories are indirect, through support for research aimed at developing and improving the skills necessary for providing virtual healthcare services.

DATA ANALYSIS

The data collected through assessments and the structured questionnaire will be organized and classified according to their variables in digital spreadsheets. Subsequently, this data will be stratified using STATA software for statistical analysis. The effects of telehealth and the occupational performance of the participants will be determined by comparing the means between the intervention and control groups, as observed in the study assessments. The analysis method will be defined as either the Student's t-test or the Wilcoxon test, depending on whether the data are parametric or non-parametric, after normality tests using Shapiro-Wilk and evaluation of histograms or q-q plots. The other objectives will be analyzed descriptively. The information obtained will be correlated with the bibliographic material collected, aiming to integrate the results and draw conclusions about the use of telerehabilitation by occupational therapists.

FINANCIAL RESOURCES

The research will not receive direct public or private funding. Expenses related to equipment, personnel, materials and supplies, among other costs necessary for the project, are already integrated into the routine of the health service. Thus, these costs will not represent an additional burden on the institution's operation.

TIMELINE

The planned research schedule will be executed, as per Table 1, if the project is approved by the CEP/CONEP System. The same will occur within a period of 11 months.

Stage Identification	Month										
	0 1	0 2	0 3	0 4	0 5	0 6	0 7	0 8	0 9	1 0	1 1
Field research - participant recruitment and randomization	X	X									
Field research - initial application of questionnaires and scales (group, intervention, and control)	X	X									

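### The group comparison ignores the baseline scores and does not say whether final or change scores are compared; pre-specified ANCOVA would settle both and is usually more precise with 10 per arm

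*Combined protocol and SAP*

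**What the plan says.** The DATA ANALYSIS section is the whole statistical plan. The effects "will be determined by comparing the means between the intervention and control groups, as observed in the study assessments". On the test it says: "The analysis method will be defined as either the Student's t-test or the Wilcoxon test", with the choice resting on Shapiro-Wilk and plots. No covariate, regression or other adjustment is mentioned anywhere, and change from baseline is never named as an outcome.

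Under METHODS, "Both groups will undergo initial assessments in the first session and final assessments in the last session". The appointment schedule in the appendices lists the IADL scale, Katz and MAL at both the first and the last visit, so every scale has a baseline value. The sample is "20 users, divided equally into two groups", and the inclusion criteria admit adults "who present with sequelae of stroke, regardless of the Rankin scale score".

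On the order of events, METHODS says: "A blind evaluator will open the sealed envelopes after the Informed Consent Form (ICF) has been signed and will conduct the evaluation". The list of stages gives the same order: "ii) randomization; iii) application of scales and structured questionnaire (intervention and control groups".

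**The concern.** There are two study assessments, so a comparison of means as observed in them may use final scores or changes from baseline. The text does not settle which. Both are unbiased on average over randomizations. In any one trial, however, they handle a chance baseline imbalance in opposite ways: the final-score comparison carries part of it into the estimate, and the change-score comparison over-corrects. With 10 patients per arm and no restriction on disability, such imbalances will often be large.

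Three things are at stake. The estimate can move materially through a choice made after the data are seen. Baseline data that are already collected go unused, so confidence intervals are likely to be wider than they need be. And a pilot's most useful product, an effect estimate with a confidence interval, is not specified. Average bias of either test is not the issue.

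**Working it through.** **Inputs.** From the documents: 20 participants, 1:1 allocation, so n = 10 per arm. The sample is one of convenience with no alpha, power, SD, effect size or correlation, so there is no stated figure to reproduce. Assumed: two-sided 5%, normal scores, equal SDs at both times (varied below), and a baseline-final correlation r over a range. All results are in SD units.

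**1. The open choice.** Write X for baseline and Y for final means in arms 1 and 0. Then

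(Y1 − Y0) − [(Y1 − X1) − (Y0 − X0)] = X1 − X0.

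The two estimates differ by the baseline difference, whatever r is. Its SD is √(2/10) = 0.447, and P(|difference| > 0.5) = 2·P(Z > 0.5/0.447 = 1.118) = 0.26.

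In a null simulation (100,000 runs), each t-test alone rejected in 4.9% to 5.1%. The chance that at least one of the two was significant was 8.8%, 9.1%, 9.4%, 9.4% and 9.6% at r = 0.3, 0.5, 0.7, 0.8 and 0.9. A separate run of 200,000 gave 9.2% to 9.6% for r from 0.5 to 0.9.

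ANCOVA removes this choice. Regressing either the final score or the change on arm and baseline gives the same arm coefficient; only the baseline slope shifts, by 1.

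**2. Precision.** Standard errors:

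- Final: 0.447, 18 df (t = 2.101)
- Change: 0.447·√(2(1 − r)), 18 df
- ANCOVA: 0.447·√((1 − r²)(1 + 1/16)), 17 df (t = 2.110), where 1/16 = 1/(20 − 4) is the cost of estimating the slope

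| | r = 0.3 | r = 0.5 | r = 0.7 | r = 0.8 |
|---|---|---|---|---|
| ANCOVA SE ÷ final SE | 0.98 | 0.89 | 0.74 | 0.62 |
| ANCOVA SE ÷ change SE | 0.83 | 0.89 | 0.95 | 0.98 |
| 95% half-width, final | 0.94 | 0.94 | 0.94 | 0.94 |
| 95% half-width, change | 1.11 | 0.94 | 0.73 | 0.59 |
| 95% half-width, ANCOVA | 0.93 | 0.84 | 0.69 | 0.58 |
| Power at 1 SD, final | 56% | 56% | 56% | 56% |
| Power at 1 SD, change | 43% | 56% | 78% | 92% |
| Power at 1 SD, ANCOVA | 57% | 66% | 82% | 93% |

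The SEs are equal at r = 0.24 (against final) and r = 0.88 (against change). Counting the lost degree of freedom, these become 0.26 and 0.87. The worst SE ratio is √1.0625 = 1.031. Against final scores it occurs at r = 0; against change scores it is approached as r nears 1 (1.018 at r = 0.95).

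**3. Unequal SDs.** Let the final SD be k times the baseline SD. The change-score variance is then proportional to k² + 1 − 2kr = k²(1 − r²) + (kr − 1)², and the ANCOVA variance to 1.0625·k²(1 − r²).

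- k = 1.25: the SE ratio is 0.97, 1.02, 1.03 at r = 0.5, 0.7, 0.8.
- k = 0.8: it is 0.78 to 0.83 over the same r.

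Since (kr − 1)² cannot be negative, the ratio never exceeds 1.031.

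**4. Error given an imbalance.** With a 0.5 SD baseline difference, the expected error is 0.5r for final scores and 0.5(r − 1) for change scores. At r = 0.5, 0.7, 0.8 that is +0.25, +0.35, +0.40 and −0.25, −0.15, −0.10 SD. For ANCOVA with a common linear slope it is 0.

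**5. Bounded scales.** Simulated scores resembling Katz (0–6), IADL (seven items scored 1–3, so 7–21) and MAL (0–5), with assumed distributions and 6,000 runs each, gave ANCOVA null rejection of 4.6% to 5.4%. At latent r = 0.7 the SD of the ANCOVA estimate was 0.75 to 0.78 of that for final scores and 0.94 to 0.95 of that for change scores. Permutation ANCOVA on Katz-like data (3,000 runs) rejected 5.0% and 4.7% under the null at latent r = 0.5 and 0.8.

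**The case against.** The strongest reply is that this is a pilot with a convenience sample and valid tests. Change from baseline is never named, so final scores are the plainer reading. On that view one sentence naming the compared score is all that is needed, and ANCOVA is an improvement in efficiency. Much of this is fair: the tests are not invalid, final scores may well be what was meant, and the 9% error rate is a worst case that nothing in the documents suggests is intended. But the section covers two assessments and does not say, and if final scores are meant, that is the comparison against which ANCOVA gains most.

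The mean-difference formulas do not describe the Wilcoxon branch. That stands. Applying the plan's Shapiro-Wilk rule to an assumed Katz-like score led to Wilcoxon in about 80% of runs for final scores, and the either-significant rate was then 7.6% to 8.9%, lower but still well above 5%. In one assumed Katz-like scenario with an effect, at r = 0.7, ANCOVA had 72% power against 50% and 56% for rank-sum tests on final and change scores. I read Wilcoxon as rank-sum because the comparison is between groups; the plan should say so.

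Against change scores the gain is small at r of 0.7 or more, and it can vanish if the final SD is larger than the baseline SD. That also stands, although the SE loss stays within about 3%. Zero conditional error needs a common linear slope, which is doubtful for a 0–6 score with floor or ceiling. Nor does baseline adjustment correct for the unequal follow-up created when a participant called to in-person care has an early final assessment.

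**Conclusion.** The concern holds. The plan leaves the compared score undefined and does not use the baseline values it collects. With 10 per arm, final-score and change-score estimates will differ by more than 0.5 SD in about one randomization in four, and choosing between them by significance would raise the t-test error from 5% to about 9%. What is left open is the estimator: for means, all three analyses target the same difference.

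The precision gain is large against a final-score test at high correlation (SE 26% lower at r = 0.7, 38% at r = 0.8) and modest against a change-score test (5% and 2% at the same r). These figures assume normal scores and equal SDs, and r is not given in the documents. The conclusion does not depend on one value of r: ANCOVA is best or within about 3% of best in SE across the range. It should be adopted before any final scores are analysed, but the planned tests are not wrong in themselves.

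**What to change.** In DATA ANALYSIS, state that for each scale the final score is analysed by ANCOVA, with arm and that scale's own baseline score as the only covariate. The adjusted mean difference and its 95% CI are the main result, whatever Shapiro-Wilk shows. MAL has a quantitative and a qualitative score, so say whether one or both are analysed, each with its own baseline.

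For the coarse, bounded Katz and IADL scores, take the p-value by permuting arm labels. State in advance that the interval leads if the two disagree; they did so at the 5% level in about 4% of Katz-like simulated runs with an effect. Keep the t-test or rank-sum test as a sensitivity analysis, with the compared score named.

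In METHODS, reorder the steps so that the baseline scales are completed before the envelope is opened. Any use of baseline, including change scores, needs this.

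The cost is one or two sentences, one regression command per analysed score in the software already planned, one residual degree of freedom (at worst about 3% on the SE) and a change in the order of two steps. No extra patients or data are needed.
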